5.7 Treatment Compliance

Study drugs, including the patient's current ADT, will be administered under the supervision of study personnel, and treatment compliance will be verified accordingly.

6 STUDY PROCEDURES AND ASSESSMENTS

All study assessments will be performed at the visits and time points outlined in the Time and Events Schedule (Table 1).

The pre-dose period on Day 1 will be considered time zero. Other logistical considerations (e.g., sequence of events, assessment windows) will be outlined in study-specific procedures. Post-Screening psychiatric scales will be administered using the timeframe since the last administration of the scale.

6.1 Study Procedures

6.1.1 Screening (Day -30 to Day -2)

After the ICF is signed, a Screening number will be assigned to the patient, and an outpatient Screening Visit will be conducted during which the patient will undergo an interview and medical assessments to determine eligibility for study participation. Patients who meet all the Screening entry criteria will be scheduled for admission to the inpatient facility.

6.1.2 Check-In (Day -1)

Inpatient admission may occur up to 30 days after the Screening Visit as soon as it is determined that patients meet all Screening criteria. Upon Check-in, patients will undergo further medical and psychiatric Screening according to the Time and Events Schedule (Table 1) to ensure they continue to qualify for participation in the study. The patient's prescribed antidepressant will be administered by site personnel while the patient is confined to the study unit.

6.1.3 Baseline (Day 1)

Assessments will be conducted according to the Time and Events Schedule (Table 1). The Baseline criteria checklist must be completed on Day 1, prior to randomization, to determine if the patient is still eligible for participation in the study. Any patient who does not meet full Screening and Baseline entry criteria must be discontinued from the study and will be considered a screen failure. Patients who meet full Screening and Baseline entry criteria will be randomized and assigned a Patient ID Number.

6.1.4 Dosing Period (Day 1 to Day 7)

The dosing period will begin on Day 1 and continue through the last dose of study drug on Day 7 (End of the Dosing Period [EDP]). Study drug will be administered in the morning. Assessments during the dosing period will include measures of safety and tolerability, PK, and efficacy. For patients who discontinue study drug prior to Day 7, all EDP assessments should be completed according to the Time and Events Schedule (Table 1) provided informed consent has not been withdrawn.

6.1.5 24-Hour Post-Dose Assessments (Day 8)

On Day 8, patients will be evaluated 24 hours after the final dose of study drug on Day 7 according to the Time and Events Schedule (Table 1). Blood samples will also be drawn for PK analysis approximately 24 hours after the last dose of study drug.

6.1.6 Discharge (Day 9)

Following the last dose of study drug, each patient (including those who discontinue from the study drug prior to Day 7) is to remain in the inpatient facility for at least 2 additional days of safety and efficacy monitoring. The assessments to be conducted prior to Discharge on Day 9 are listed in the Time and Events Schedule (Table 1). Blood samples will also be drawn for PK analysis prior to Discharge on Day 9.

6.1.7 Outpatient Observation Period (Day 10 to Day 14)

The End of the Observation Period (EOP) will occur on Day 14 when the EOP interview will be conducted in person to assess psychiatric symptoms and safety endpoints, including medical conditions, new medications, and newly emergent AEs as listed in the Time and Events Schedule (Table 1). A confirmatory pregnancy test will be administered. Blood samples will also be drawn for PK analysis approximately 168 hours after the last dose of study drug. For patients who discontinue study drug prior to Day 7, the EOP interview will occur 7 days after their last dose of study drug. (The window for the EOP visit is ± 3 days.)

6.1.8 Follow-Up Period (Day 15 to Day 21)

Follow-up interviews will be conducted with all patients (including those who discontinue from the study drug prior to Day 7) 14 days after their last dose of study drug. (The visit window is ± 3 days). In the Follow-Up interview (Day 21), C-SSRS, AEs, and medications will be recorded (Table 1). This interview may be conducted by telephone. A confirmatory pregnancy test will be administered if the visit is conducted at the site. During the Follow-Up Period, safety evaluations should be conducted, at the discretion of the Investigator, to evaluate any unresolved abnormal treatment-emergent findings.

6.2 Safety Assessments

Safety assessments will be performed at the time points indicated in the Time and Events Schedule (Table 1).

6.2.1 Vital Signs

Routine vital sign parameters will be measured at Screening and Check-in (Day -1), pre-dose and 1 hour post-dose on Day 1, pre-dose on Day 2 through Day 7, once on Day 8, prior to Discharge on Day 9 and on Day 14. Vital signs should be measured after the patient has been in a supine or semi-supine position for at least 3 minutes. Vital signs will include blood pressure (BP, systolic and diastolic, mmHg), heart rate (HR, pulse rate [bpm]), pulse oximetry, and respiratory rate (RR, breaths/minute). Measurement of orthostatic BP should follow measurement of supine or semi-supine BP. Patients should be asked to stand for 3 minutes before measurement of orthostatic BP. The BP cuff should be kept in place between supine and orthostatic BP measurements. Blood pressure should be recorded to the nearest 2 mmHg mark on the manometer or to the nearest whole number on an automatic device.

6.2.2 Weight and Body Temperature

Weight and oral body temperature ($^{\circ}\text{C}$) will be recorded at Screening, Check-in (Day -1), EDP (Day 7), and EOP (Day 14).

6.2.3 Physical Examination

The physical examination, assessing the patient's overall health and physical condition, will be performed at Screening, Check-in (Day -1); Day 7 and prior to Discharge (Day 9). The patient's BMI will be calculated at Screening. Height will be recorded at Screening only.

6.2.4 12-Lead Electrocardiograms (ECGs)

12-Lead ECGs will be performed at Screening; at Check-in (Day -1); 1 hour pre-dose and 2 hours, 4 hours, 6 hours, and 8 hours post-dose on Day 1 and Day 2; daily 2 hours post-dose on Day 3 through EDP (Day 7); on Day 8; prior to Discharge on Day 9; and at EOP (Day 14). Electrocardiograms will be performed in triplicate at each time point (e.g., 3 separate 10-second ECG recordings collected at intervals of approximately 1 minute apart, but within 5 minutes).

Electrocardiograms will be performed with the electrodes positioned on the torso after the patient has been resting in a supine or semi-supine position for at least 3 minutes. The ECG will electronically measure and calculate ventricular HR and the PR, QRS, measure of the time between the start of the Q wave and the end of the T wave in the heart's electrical cycle (QT), and QTc intervals. The Fridericia formula will be used for QTc. Triplicate ECGs will be averaged in the database for data analysis.

ECGs will be submitted electronically to central ECG reading center for evaluation of subject for entry into the study. The Investigator will make a final judgment on whether to include the subject's ECGs meets the entry criteria for the study.

At the discretion of the Investigator, a standard 12-lead ECG with conventional lead placement may be performed at any time during the study (e.g., in case potential ischemia or any cardiac abnormality is observed).

6.2.5 Clinical Laboratory Assessments

Clinical laboratory tests (chemistry, hematology, and urinalysis) will be conducted at Screening, Check-in (Day -1), EDP (Day 7), and EOP (Day 14) unless otherwise noted. Blood and urine samples will be collected, processed, and shipped according to the research site's SOPs and instructions from the safety laboratory. All laboratory safety data will be reviewed by the Investigator or designee for clinical significance.

Blood volumes required per draw, laboratory test, and study phase are available in Appendix 11.1. Additional laboratory samples may be taken at the discretion of the Investigator or designee (e.g., if the results of any tests fall outside reference ranges or clinical symptoms necessitate testing to ensure safety).

6.2.5.1 Clinical Chemistry

Quantitative analysis will be performed for the following analytes: alkaline phosphatase, albumin, calcium, chloride, creatinine, random glucose, potassium, magnesium, ALT, AST, gamma-glutamyl transferase (GGT), lactate dehydrogenase, sodium, total bilirubin, urea, and testosterone.

6.2.5.2 Hematology

A peripheral blood smear will be performed to assess blood cell morphology. Quantitative analysis will be performed for at least the following analytes: hemoglobin, hematocrit, red blood cell count (RBC), white blood cell (WBC) count, WBC differential (absolute counts), and numerical platelet count.

6.2.5.3 Urinalysis

Qualitative or quantitative analysis will be performed for the following analytes, as appropriate: specific gravity, pH, ketones, glucose, nitrite, blood, leukocyte esterase, protein, urobilinogen, and bilirubin. If nitrite, blood, or protein tests are positive, a microscopic examination will be performed.

6.2.5.4 Thyroid Panel

A thyroid panel will be evaluated at Screening to identify patients with clinically significant abnormal laboratory results for TSH, T3, and T4.

6.2.5.5 Viral Screen

Serology will screen for hepatitis B, hepatitis C, and HIV at Screening. Patients with negative viral serology tests for hepatitis B and HIV will be eligible for the study. Positive hepatitis C values will be reviewed for eligibility on a case by case basis by the Medical Director. Positive results will be managed according to local regulatory requirements and the site's SOPs.

6.2.5.6 Breath Alcohol

Breath alcohol testing will be performed according to the site's SOPs at Screening, Check-in (Day -1), and Day 14. If there is any doubt or concern regarding alcohol use, research site staff may request a breath test for alcohol measures at any time during the study.

6.2.5.7 Drugs of Abuse Screen

A urine drug test will be conducted at Screening and Check-in. The urine drug screen will test for following drugs of abuse: tetrahydrocannabinol, opiates (including oxycodone), amphetamines, cocaine, and benzodiazepines.

6.2.5.8 Pregnancy Testing

A urine pregnancy test and a serum follicle stimulating hormone (FSH) test will be administered to all female patients at Screening (Day -30 to Day -2). Negative test results are required for enrollment in the study. Another negative urine pregnancy test will be required at Check-in (Day -1) for confirmation. Additional confirmatory pregnancy tests will be administered at the End of the Observation Period Visit (Day 14 ± 3 days and Follow-Up Visit (Day 21 ± 3 days).

6.2.6 Other Safety Assessments

6.2.6.1 Clinical Administered Dissociative States Scale (CADSS)

The Clinical Administered Dissociative States Scale (CADSS) will be measured at 30 to 60 minutes pre-dose on Day 1, 2 hours post-dose on Day 1, 2 hours post-dose on Day 7, and prior to Discharge on Day 9.

6.2.6.2 Columbia-Suicide Severity Rating Scale (C-SSRS)

The C-SSRS will be measured at Screening and Check-in (Day -1); at pre-dose on Day 1 and Day 2; and on Day 8, Day 9, EOP (Day 14) and EOS (Day 21).

6.2.6.3 The Clinical Opiate Withdrawal Scale (COWS)

The COWS will be measured on Day 8, Day 9, and EOP (Day 14).

6.2.6.4 4-Item Positive Symptom Rating Scale (4-Item PSRS)

The 4-Item PSRS will be measured at 30 to 60 minutes pre-dose at Baseline (Day 1), 2 hours post-dose on Day 1 (after first dose), 2 hours post-dose on Day 7 (EDP) (after last dose), and prior to Discharge on Day 9.

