6.6.3.3 Clinical Opiate Withdrawal Scale (COWS)

Safety assessments have been included to monitor for any opioid-related effects. The COWS is a clinician-administered instrument that rates 11 common opiate withdrawal signs or symptoms. The summed score of the 11 items can be used to assess a patient's level of opiate withdrawal and to make inferences about their level of physical dependence on opioids.⁴⁵

6.6.3.4 4-Item Positive Symptom Rating Scale (4-Item PSRS)

The 4-Item PSRS was adapted from the Brief Psychiatric Rating Scale developed by Ventura and colleagues. It is a clinician-administered scale intended to assess the extent to which a subject is

currently experiencing positive psychotic symptoms. The scale assesses paranoia and hallucinations as well as some specific issues related to difficulty thinking and having unusual thoughts. When administering the scale, the rater enters a number for each of 4 symptom constructs with scores that range from 1 (not present) to 7 (extremely severe). Total score on the 4-Item PSRS can range from 4 to 28. ^{46,47}

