7.1.3 Clinical Laboratory Abnormalities and Other Abnormal Assessments

Abnormal laboratory findings (e.g., from clinical chemistry or hematology tests or urinalysis) or other abnormal assessments (e.g., from vital signs, ECGs, C-SSRS, 4-Item PSRS, CADSS, COWS) judged as clinically significant by the Investigator or designee will be recorded as AEs or SAEs if they meet the definitions provided in Section 7.1.1 and Section 7.1.2. Furthermore, abnormal laboratory findings or other abnormal assessments present at Baseline that significantly worsen following the start of the study (i.e., become clinically significant) will be reported as AEs or SAEs. However, abnormal laboratory findings present at the start of the study that do not worsen will not be reported as AEs or SAEs.

The Investigator will exercise his or her medical and scientific judgment in deciding whether an abnormal laboratory finding or other abnormal assessment is clinically significant.

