The effectiveness of the patient's prescribed antidepressant medication will be assessed using the MINI, ATRQ, and HAM-D-17. The MINI will be conducted at Screening only, while the ATRQ and HAM-D-17 will be conducted at both Screening and Check-in (Day -1).

The mental status of patients will be further evaluated with the C-SSRS, CADSS, and COWS. The C-SSRS will be conducted at Screening, Check-in (Day -1), Baseline (Day 1, first day of dosing), Day 2 (24 hours after first dose), Day 8 (24 hours after last dose), Discharge (Day 9), Day 14 (EOP), and Day 21 (Follow-up). The 4-Item PSRS will be measured at 30 to 60 minutes pre-dose at Baseline (Day 1), 2 hours post-dose on Day 1 (after first dose), 2 hours post-dose on Day 7 (EDP) (after last dose), and prior to Discharge on Day 9. The CADSS will be measured at 30 to 60 minutes pre-dose at Baseline (Day 1), 2 hours post-dose on Day 1 (after first dose), 2 hours post-dose on Day 7 (after last dose), and prior to Discharge on Day 9. The COWS will be conducted on Day 8 (24 hours after the final dose of study drug), on Day 9 (Discharge), and at EOP (Day 14).

The Investigator or designee will contact each patient by telephone on Day 21 (14 days after the last dose of study drug) to assess C-SSRS, ask about AEs and evaluate the patient's general status.

The number of patients in each of the treatment groups will be presented, in addition to the number of patients who complete each visit. The reasons for all post-randomization discontinuations will be tabulated and grouped by treatment group and all patients combined. All deviations related to study inclusion or exclusion criteria, conduct of the study, patient management, or patient assessment will be described.

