11.5 Clinical Opiate Withdrawal Scale (COWS)

Clinical Opiate Withdrawal Scale (COWS)
Flowsheet for measuring symptoms over a period of time during buprenorphine induction.

For each item, write in the number that best describes the patient's signs or symptom. Rate on just the apparent relationship to opiate withdrawal. For example: If heart rate is increased because the patient was jogging just prior to assessment, the increased pulse rate would not add to the score.

Patient Name: _____		Date: _____			
Buprenorphine Induction: _____					
Enter scores at time zero, 30 minutes after first dose, 2 hours after first dose, etc.		Times of Observation:			
Resting Pulse Rate: Record Beats per Minute					
Measured after patient is sitting or lying for one minute					
0 = pulse rate 80 or below		• 2 = pulse rate 101-120			
1 = pulse rate 81-100		• 4 = pulse rate greater than 120			
Sweating: Over Past 1/2 Hour not Accounted for by Room Temperature or Patient Activity					
0 = no report of chills or flushing					
1 = subjective report of chills or flushing		• 3 = beads of sweat on brow or face			
2 = flushed or observable moistness on face		• 4 = sweat streaming off face			
Restlessness Observation During Assessment					
0 = able to sit still					
1 = reports difficulty sitting still, but is able to do so		• 3 = frequent shifting or extraneous movements of legs/arms			
		• 5 = Unable to sit still for more than a few seconds			
Pupil Size					
0 = pupils pinned or normal size for room light					
1 = pupils possibly larger than normal for room light		• 2 = pupils moderately dilated			
		• 5 = pupils so dilated that only the rim of the iris is visible			
Bone or Joint Aches if Patient was Having Pain Previously, only the Additional Component Attributed to Opiate Withdrawal is Scored					
0 = not present					
1 = mild diffuse discomfort		• 2 = patient reports severe diffuse aching of joints/muscles			
		• 4 = patient is rubbing joints or muscles and is unable to sit still because of discomfort			
Runny Nose or Tearing Not Accounted for by Cold Symptoms or Allergies					
0 = not present					
1 = nasal stuffiness or unusually moist eyes		• 2 = nose running or tearing			
		• 4 = nose constantly running or tears streaming down cheeks			
GI Upset: Over Last 1/2 Hour					
0 = no GI symptoms					
1 = stomach cramps		• 3 = vomiting or diarrhea			
2 = nausea or loose stool		• 5 = multiple episodes of diarrhea or vomiting			
Tremor Observation of Outstretched Hands					

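### COWS has no pre-dose rating, so within-patient change cannot be calculated and the worsening-from-Baseline adverse event rule in section 7.1.3 cannot be applied to it

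*Combined protocol and SAP*

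**What the plan says.** Section 6.2.6.3 sets the schedule: "The COWS will be measured on Day 8, Day 9, and EOP (Day 14". Section 8.1.5 repeats it and fixes the timing of the first rating: "The COWS will be conducted on Day 8 (24 hours after the final dose of study drug". Table 1 marks the same three days and no earlier one.

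Section 6.6.3.3 says that the scale "rates 11 common opiate withdrawal signs or symptoms", and on its use: "The summed score of the 11 items can be used to assess" the level of withdrawal and to draw inferences about physical dependence. Sections 2.1 and 8.1.3.1 list COWS among the primary safety and tolerability measures.

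The companion scales are handled differently. Section 6.2.6.1 says that CADSS "will be measured at 30 to 60 minutes pre-dose on Day 1"; section 6.2.6.4 gives the 4-Item PSRS the same slot; section 6.2.6.2 has C-SSRS at Screening, Check-in and pre-dose on Day 1.

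Section 7.1.3 names COWS among the non-laboratory assessments that can give rise to an adverse event, and includes "other abnormal assessments present at Baseline that significantly worsen following the start of the study" among those to be reported.

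**The concern.** The earliest COWS rating follows seven doses, so Day 8 cannot stand in for a baseline. Two things the plan would ordinarily rely on are therefore unavailable: a within-patient change, and the reference value that the worsening limb of section 7.1.3 presupposes. The form (section 11.5) also looks back to an earlier state on bone or joint aches, where for patients with previous pain "only the Additional Component Attributed to Opiate Withdrawal is Scored".

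This matters more than usual because of the population. Entry requires a HAM-D-17 total of at least 19, and the protocol's own depression scales (HAM-D-17 and SDQ) score anxiety, agitation, aches, gastrointestinal complaints and palpitations; HAM-D-17 also scores sweating. COWS scores pulse, sweating, restlessness, aches, gastrointestinal upset and anxiety or irritability. The two completed REL-1017 studies enrolled healthy subjects, so their finding of no withdrawal gives no background COWS level for depressed patients on antidepressants. COWS is also the only scale in the protocol used to infer physical dependence.

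**Working it through.** The plan states no power, SD or precision target for COWS, so there is no figure of its own to reproduce.

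**1. Schedule.** Table 1, section 6.2.6.3 and section 8.1.5 all give Days 8, 9 and 14. No pre-dose COWS appears elsewhere. The gap is consistent and is not a slip in one place.

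**2. What a low total can consist of.** From the form in section 11.5, the 11 item maxima sum to 4+4+5+5+4+4+5+4+4+4+5 = 48, and totals of 5 to 12 carry the label mild. Pulse 81-100 (1), reported chills or flushing (1), reported difficulty sitting still (1) and nausea (2) give 1+1+1+2 = 5. None of these is specific to withdrawal. They reach 5 only if the rater attributes each one to withdrawal.

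**3. How well the placebo arm fixes the background.** Inputs: 20 per arm (sections 3.2 and 8.2); the background proportion with COWS of 5 or more is assumed, since the documents give none. Background alone would put 40 × p active patients at or above 5. The power is for one active arm against placebo, Fisher's exact test, two-sided 0.05 (an assumed level).

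| Assumed background p | Expected among 40 active | Power, 20-point excess | Power, 40-point excess |
|---|---|---|---|
| 5% | 2 | 30% | 82% |
| 10% | 4 | 24% | 74% |
| 20% | 8 | 19% | 65% |
| 30% | 12 | 16% | 60% |

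**4. What a baseline would add to the group comparison.** In units of the post-dose SD, the standard error of a difference between two arms of 20 is √(2/20) = 0.316, and the 90% half-width is 1.645 × 0.316 = 0.52. The 90% level is borrowed from the efficacy analysis in section 8.1.4.5; no interval is planned for COWS. Let ρ be the assumed correlation between pre-dose and post-dose scores.

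- Baseline as covariate: multiply by √(1−ρ²).
- Raw change score, equal SDs at both times: multiply by √(2(1−ρ)).

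| ρ | Covariate: factor | Covariate: half-width | Raw change: variance factor | Raw change: half-width |
|---|---|---|---|---|
| no baseline | 1 | 0.52 | – | – |
| 0.3 | √0.91 = 0.954 | 0.50 | 1.4 | 0.62 |
| 0.5 | √0.75 = 0.866 | 0.45 | 1.0 | 0.52 |
| 0.7 | √0.51 = 0.714 | 0.37 | 0.6 | 0.40 |

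Covariate adjustment never does worse here, ignoring the degree of freedom it uses. A raw change score loses precision below ρ = 0.5 and gains nothing at 0.5.

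**The case against.** The strongest reply is that this is a randomized, double-blind trial. About 20 placebo patients follow the same COWS schedule (section 3.2), all patients continue their antidepressant (section 5.2), the objective is a comparison with placebo (section 2.1), and safety data are summarized by treatment (section 8.1.4.1). Pre-existing symptoms are equal across arms in expectation. This stands. A reader might infer that background symptoms cannot be told apart from withdrawal at all; at group level they can, without bias, though imprecisely.

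The form also guards against over-scoring. Its general instruction is "Rate on just the apparent relationship to opiate withdrawal", and the lowest non-zero anxiety level requires a patient to report that irritability or anxiety is rising, which stable anxiety would not meet. Other pre-dose data help: heart rate (section 6.2.1), SDQ items on agitation, anxiety, palpitations, aches and gut symptoms, MADRS inner tension, and pre-dose events recorded as baseline signs and symptoms (section 7). So the further inference that an individual total of 5 or more is uninterpretable also goes too far. What remains is that attribution needs a reference point, that the same rater is used only where possible (section 4.6), and that none of these data yields a COWS change.

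The severity bands appear only on the form; no endpoint or planned table classifies patients by them. Safety analysis is descriptive and the study is not powered for signal detection (section 8.2). Patients with a confirmed positive drug screen are excluded, and others rated only for apparent withdrawal before any study drug might score near zero, which could make ρ small. These points limit the precision argument. They do not answer the section 7.1.3 problem or the missing individual change, and safety data are to be listed by patient.

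**Conclusion.** The point holds as a minor, inexpensive improvement. Individual COWS change cannot be calculated, and one limb of the section 7.1.3 reporting rule names a scale that has no Baseline. The other limb, reporting on the investigator's judgement of clinical significance, still works. The documents do not support reading this as a bias in the comparison with placebo.

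The gain is mainly in interpreting individual scores. The precision gain is secondary and depends on an unknown correlation: negligible at 0.3 (0.52 to 0.50 SD), modest at 0.5 (0.45 SD) and useful at 0.7 (0.37 SD), and only with covariate adjustment. These figures assume 20 patients rated per arm, equal SDs across arms and a normal approximation. The background rates in the power table are assumptions too.

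**What to change.** Add one pre-dose COWS on Day 1, in the slot where CADSS and the 4-Item PSRS are already rated, and enter it in section 6.2.6.3, Table 1 and section 8.1.5. List each patient's change from Baseline on Days 8, 9 and 14, and summarize those days by arm. For any between-arm comparison, use the Baseline COWS as a covariate rather than a raw change score. With that value recorded, section 7.1.3 can be applied to COWS as written.

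If the schedule cannot be changed, plan an active-versus-placebo COWS summary by visit, state the missing Baseline as a limitation, and reconcile section 7.1.3 with the schedule.

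The cost is a few minutes of existing rater time per inpatient and a small edit to three places. No visit is added.
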